3.5.1. Sample size and power calculations

For the first objective, to compare the performance of the algorithms, the sample size has been calculated for the three indicators defined above. We used the percentage of HPV positive women with HSIL+ who were treated for the sample size calculation as it is the indicator that requires the largest sample size.

For HIV positive women, we assumed several features as follows: HPV testing sensitivity of 95%, 85% eligibility for ablative treatment and an overall attrition of 20% for both arms. Additionally, for Arm 1 (HPV+VIA), we assumed a VIA sensitivity among HPV positive women of 75% and 4% VIA result of suspected cancer or VIA inadequate. Using a randomisation ratio of 4:1 to Arm 1 and Arm 2, we will need to detect 125 histological HSIL+ cases in Arm 1 and 25 histological HSIL+ cases in Arm 2.

With 3000 HIV positive women attending screening, assuming 50% HPV positivity [24-26] and 50% VIA positivity, and a prevalence of 5% HSIL we will have at least 85% power to detect a difference of 24% (72.8% in Arm 1 vs 97% in Arm 2) with two-sided type error I 0.05 (see Table 2 and Table 3). In summary, under all assumptions stated, 1500 HPV positive women will need to be included.

Outcomes	Total	Arm VIA (1)	Arm HPV (2)	Difference
Total HSIL+ cases (n)	150	120	30	
Total HSIL+ HPV positive cases (n)	143	114	29	
Total HSIL+ treated (n)	111	83	28	
Total <hsil treated
(overtreatment) (n)</hsil>	742	487	254	
% of treatment among HSIL+ HPV positive women		72.8%	97.0%	24%
% of overtreatment among HPV positive women		41%	85%	44%

Table 2. Differences expected according to number of histological HSIL+ cases treated and<HSIL women overtreated in HIV positive women	Table 3. Number of HIV positive women to be screened

Sample size	Parameter	n arm VIA (1)	n arm HPV (2)
Prevalence of HSIL+	0.05		
Expected number of HIV positive women (n)	3000	2400	600
Power	>85%		

Similarly for HIV negative women, randomising in a 3:1 ratio to Arm 1 or Arm 2, under the same assumptions for sensitivities (HPV 95%, HPV, VIA 75% in HPV positives, 85% eligibility for ablative treatment in Arms 1 and 2, and 20% attrition overall), we will need to detect 113 HSIL+ cases in Arm 1 and 38 in Arm 2 to compare the percentage of women with HSIL+ treated under each algorithm. With a sample size of 7500 HIV negative women, assuming 15% HPV prevalence [27], 50% VIA positivity, 2% prevalence of HSIL+, and two-sided type error I of 0.05, we will have at least 85% power to detect a difference of 24% (72.8% in Arm 1 and 97% in Arm 2) in the percentage of HPV positive women with HSIL+ treated (see Table 4 and Table 5). In summary, under all the assumptions stated, 1125 HIV negative HPV positive women will need to be included.

Outcomes	Total	Arm VIA (1)	Arm HPV (2)	Difference
Total HSIL+ cases (n)	150	113	38	
Total HSIL+ HPV positive cases (n)	143	107	36	
Total HSIL+ treated (n)	112	78	35	
Total <hsil treated
(overtreatment) (n)</hsil>	553	323	230	
% of treatment among HSIL+ HPV positive women		72.8%	97.0%	24%
% of overtreatment among HPV positive women		38%	82%	43%

Table 4. Differences expected according to number of HSIL+ cases treated and <HSIL women	overtreated in HIV negative women

Table 5. Number of HIV negative women to be screened and randomized

Sample size	Parameter	Arm VIA (1)	Arm HPV (2)
Prevalence of HSIL+	0.02		
Expected number of HIV negative women (n)	7500	5625	1875
Power	>85%		

3.6. Ancillary studies

We will obtain aliquots from HPV samples from participants in the study that will be stored at -80C. These samples can later be used to evaluate the performance of novel screening and triage methods for cervical cancer (HPV genotyping, oncoprotein tests, automated visual evaluation (AVE), and others).

3.7. CESTA Module 2: Randomized controlled trial to compare the cure rate of CIN2+ in HIV positive women treated by thermal ablation and cryotherapy (see figure 4)

3.7.1. Primary Objectives:

To compare the CIN2/3 cure rates of treatment with cryotherapy and thermal ablation
12 months after the treatment in HIV positive women.

2. To model the cost-effectiveness of treatment of CIN2/3 by cryotherapy *vs.* thermal ablation in HIV positive populations.

3.7.2. Secondary Objectives:

- 1. To compare the CIN2/3 cure rates of cryotherapy and TA 24 months after the treatment in HIV positive women.
- 2. To compare the histological HSIL cure rate of cryotherapy and TA after 12 and 24 months.
- 3. To assess patient adherence to study visits in clinics using SEVIA or not.
- 4. To assess the performance of VIA as a test of cure 1 year after treatment.
- 5. To estimate the HPV infection clearance rate after one year of the treatment.
- 6. To describe the safety and side effects of cryotherapy and thermal ablation.
- 7. To assess and compare the HIV shedding among women treated with cryotherapy and thermal ablation.

3.8. Study outline CESTA Module 2

The CESTA Module 2 is a randomised controlled trial to compare the cure rate of cryotherapy to thermal ablation HIV positive women. Women with diagnosed cytological LSIL+ (LSIL; HSIL; or ASC-H) at one of the estimated 8-9 involved ARV clinics in South Africa, all situated preferably around Durban, will be invited to one of the CESTA clinics. A total of 920 HIV positive women with CIN2/3 will need to be included in this module to obtain sufficient study power (see section 3.10.1). Some estimated 143 women will already be detected with CIN2/3 in the CESTA Module 1 and can therefore be invited to participate in the CESTA Module 2. This mean that we estimate that CESTA module 2 will need to identify another 777 women with CIN2/3.

Since 2018, women are routinely screened at ARV clinics with liquid based cytology every 3 years in South Africa. We will access the results of those women already screened at the clinics with permission of the clinics administration and the women themselves.

Women with LSIL+ will attend the closest CESTA study clinic. After informed giving written informed consent, the nurse will take some short questionnaires on demographics and sexual history, and socio-economic characteristics. A health economics questionnaire focused on

participant travel time and expenditures will also be administered. The nurse will collect 2-4 biopsies, with the same procedure as described under Module 1 (section 3.2.1.). Women will then receive an appointment for an additional biopsy results visit. At that visit, all women with CIN2 or 3 without glandular lesions and eligible for ablative treatment through VAT will be randomized in a 1:1 ratio into cryotherapy and thermal ablation, performed by the nurse at the same visit after taking 2-3 pictures with the SEVIA application. Ablation ineligible women will be referred to colposcopy and will be managed and treated appropriately including LLETZ. Women with normal or CIN1 biopsy results will be exited from the study and referred back to the ARV clinic to follow the South Africa standard care recommendations, i.e. rescreening after 1 year.

The VAT examination is inadequate if the SCJ is not completely seen and in that case, the nurse will obtain an endocervical brush for cytology and the women will be sent to the colposcopist when the cytology results are available.

Similarly as in Module 1 (section 3.2.1), women who receive treatment will be called by telephone 1 and 4 weeks after treatment and answer a questionnaire on perceived side-effects and acceptability of treatment. The nurse will take the necessary actions if serious side-effects are reported.

In addition, all treated women will be recalled at 12 and 24 months for a follow-up visit including HPV testing, VIA, colposcopy and biopsy on all HPV positive women, and those with CIN2+ will be treated as appropriate. The SEVIA application will also be used for quality control of the VAT by the nurse, and for patient navigation, as described in Module 1.

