HIV positive women will be recruited from HIV care clinics, also called antiretrovirals (ARV) clinics in the Durban area, South Africa. After giving informed consent, women will be screened with HPV testing and those that are HPV positive will be randomized at a 4:1 ratio into HPV + VIA + treat (Arm 1) and HPV + treat (Arm 2) in 1 of the 2 CESTA study clinics. Women in Arm 1 will receive VIA and only positive for VIA will be treated. In Arm 2, all HPV positive women will be treated. Women that are eligible for ablative treatment will be randomized into treatment with TA or cryotherapy in both arms. Others will be referred to colposcopy. After VIA in Arm 1 or before treatment in Arm 2, the nurses will collect 2-4 biopsies on all HPV positive women. The biopsies will be used as gold standard for disease detection. The first 200 women treated will be followed up intensely for 4 weeks to assess side-effects and levels of HIV shedding. Subsequently treated women will be called by telephone after 1 week and 1 month to assess side-effects and satisfaction with the procedures. Smartphone enhanced VIA (SEVIA) with patient navigation will be used in 1 of the 2 study clinics. 2-3 Pictures are taken with the SEVIA smartphone tool after application of acetic acid to the cervix. The pictures are sent in a secure way to expert reviewers who provide feed-back to the nurse in real time. The application can also be used to track adherence of the

women to the screen and treat procedures or referral and send automated reminders of appointments. Outcomes on performance of VIA and patient adherence will be compared between study clinic that uses SEVIA and the one not using SEVIA. All women who were HPVpositive or were treated will be called back after 1 year for a follow-up visit. Women will be screened with HPV testing and VIA and 2-4 colposcopy-directed biopsies will be taken from all HPV positive women. Women with remaining/recurrent CIN2+ disease will receive appropriate management.

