HIV negative women will be recruited from the communities in the Dakar area. They will be screened in 1 of 4 CESTA study clinics. Procedures will be similar as in HIV positive women, except that the randomization rate will be 3:1 for Arm 1 and Arm 2 and that the women eligible for ablative treatment will be all treated with TA. SEVIA will be applied in 2 of the 4 study clinics to compare SEVIA outcomes in those clinics using it or not. Follow-up of treatment side-effects and women's satisfaction will be by telephone after 1 week and after 1 month. Similar to HIV positive women, all HPV positive women or those treated will be invited for a 1-year follow-up visit with the same procedures as described above.

The cost-effectiveness study will answer questions on the comparative value and efficiency of the two screening arms and two treatments respectively, using epidemiological data collected through the clinical study for the effectiveness portion of the analysis. Cost data collected through questions embedded in the clinical questionnaires and by more in-depth but limited interview will be supplemented by administrative data where necessary to form the cost portion of the analysis. The study will use a well-validated cervical cancer model.

Module 2 will study the main objectives 2 and 3 among 920 HIV positive women with CIN2/3 in South Africa. An estimated 143 women will have CIN 2/3 on biopsy from Module 1 and can be directed to participate in Module 2. A remaining 777 women with CIN2/3 will need to be recruited through 8-9 ARV clinics. Since 2018, women are screened routinely with liquid based cytology (LBC) in South Africa. We will invite women with LBC results of low-grade squamous intraepithelial lesions or worse (LSIL+) to participate in the CESTA Module 2 study in 1 of the 2 CESTA study clinics dedicated to Module 2. After giving informed consent, 2-4 cervical biopsies will be taken by the study nurses. Women with biopsy results <CIN2 will be referred back to the ARV clinic for routine cervical cancer screening. Women with CIN2/3 and that are eligible for ablative treatment will be randomized into TA and cryotherapy. Others will be referred to

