Each of the aims will be evaluated in different modules: Mod 1, a randomised controlled trial (RCT) to compare the efficacy of the two screen-and-treat algorithms, and Module 2, another

RCT to compare the 12 and 24 months CIN2+ cure rates of each ablative treatment. The first module will be carried out among HIV positive and HIV negative women in South Africa and Senegal, respectively. The comparison will be based on HPV positive women with histological high grade squamous intraepithelial lesions or worse (HSIL+) adequately treated, those left untreated and those who were treated and did not have confirmed disease (overtreatment) randomized to each algorithm.

The second module will be carried out in HIV positive women with histologically diagnosed CIN2/3 at the time of randomization. The third aim on cost-effectiveness will be evaluated within each module to provide a complete picture on cervical cancer screening strategies in the context of the cervical cancer elimination initiative.

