- 9. To explore the acceptability of thermal ablation versus cryotherapy among treated women.

3.2. Study outline CESTA Module 1

The CESTA Module 1 is a double-level randomized study with the main objective to evaluate the efficacy of two cervical screen-and-treat algorithms in HIV positive and HIV negative women separately.

3.2.1. CESTA Module 1 among HIV positive women in South Africa (see figure 2)

3000 HIV-positive women will be screened with HPV testing and HPV-positive women will be randomized in a 4:1 ratio to be triaged by VIA and treated (arm 1, HPV+VIA+treat) or treated right away (arm 2, HPV+treat).

The study will recruit women aged 25-54 years. Recruitment will be done mainly in HIV care clinics in South Africa. After informed consent, women will be administered short questionnaires on demographics and sexual history, and socio-economic characteristics. A health economics questionnaire focused on participant travel time and expenditures will also be administered. Women will then be asked to self-collect a vaginal sample and afterwards, a nurse will collect a cervical sample, both samples will be used for HPV testing. Any woman who refuses consent or opts out after consent will be referred to routine cervical cancer screening.

Participants will be given an appointment to the CESTA study clinics to collect their HPV result. HPV positive women will be randomised to arms 1 or 2 using the envelop method with preprinted assignment cards.

ARM 1:

A nurse will carry out a speculum examination and collect an endocervical swab to measure HIV shedding. She will then perform VIA and in half of the CESTA study clinics, the nurse will take 2-3 pictures of the cervix using the SEVIA smartphone application. 2-4 biopsies will be collected at the squamo-columnar junction (SCJ) from all quadrants that show aceto-white changes or at 12 and 6 'o clock if no acetowhite changes are visible. All eligible women for ablative treatment will be further randomised to sub-arms A (cryotherapy) and B (thermal ablation).

VIA positive women not eligible for ablative treatment will be referred to the colposcopy clinic for appropriate referral and management.

The VIA examination is inadequate if the SCJ is not entirely visible. In this case, an endocervical brush will be collected for cytological examination and the woman will be referred to colposcopy once the cytology result is known.

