Women with CIN2+ on biopsy who have not been treated based on screening results from arm 1 will also be randomised to sub-arms A and B if eligible for ablative treatment or referred to colposcopy otherwise.

ARM 2:

Study procedures in this arm are mostly similar to Arm 1. A nurse will carry out a speculum examination and collect an endocervical swab to measure HIV shedding. She will then perform a visual assessment for treatment using acetic acid (VAT, see section 2.4) to assess if the patient is eligible for ablative treatment and in half of the study clinics, 2-3 pictures will be taken with the SEVIA App. After VAT, 2-4 biopsies will be collected at the SCJ from all quadrants that show aceto-white changes or at 12 and 6 'o clock if no acetowhite changes are visible.

All women that are eligible for ablative treatment will be treated and randomised into subarm A (cryotherapy) and sub-arm B (thermal ablation) as in Arm 1; women with VAT not eligible for ablative treatment will be referred to the colposcopy clinic for appropriate referral and management.

Similar as for VIA, the VAT examination is inadequate if the SCJ is not entirely visible. In this case, an endocervical brush will be collected for cytological examination and the woman will be referred to colposcopy once the cytology result is known.

In both arms, endocervical sample collection for HIV shedding will be done after 1, 2, 3, and 4 weeks in 100 women (each arm) who received treatment (modes of selection for these women still needs to be decided). At those respective visits, women will answer a questionnaire on perceived side-effects and acceptability of treatment. Women who do not come back for HIV shedding sample collection will be called by telephone after 1 week and 1 month to assess perceived side-effects and acceptability of treatment. The nurse will take the necessary actions if serious side-effects are reported.

In addition, all treated women will be recalled at 12 months for a follow-up visit including HPV testing, VIA with colposcopy and biopsy on HPV positive women, and those with CIN2+ will be treated as appropriate.

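### Does crediting all 143 expected Module 1 cases to Module 2 leave the cure-rate comparison short of power, when most of them are randomised and ablated before histology?

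*Protocol*

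**What the plan says.** The Executive Summary states the credit as "An estimated 143 women will have CIN 2/3 on biopsy from Module 1 and can be directed to participate in Module 2", and section 3.8 repeats it: "Some estimated 143 women will already be detected with CIN2/3 in the CESTA Module 1 and can therefore be invited to participate". Sections 3.8 and 3.9.1 subtract 143 from 920 to reach 777.

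The end of section 2.1 describes the population: "The second module will be carried out in HIV positive women with histologically diagnosed CIN2/3 at the time of randomization". Section 3.8 places randomisation at the biopsy-results visit: "At that visit, all women with CIN2 or 3 without glandular lesions and eligible for ablative treatment through VAT will be randomized".

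Module 1 in South Africa runs in a different order. The Executive Summary says "After VIA in Arm 1 or before treatment in Arm 2, the nurses will collect 2-4 biopsies on all HPV positive women". Under section 3.2.1, ablation-eligible Arm 1 women (VIA-positive, as the Executive Summary makes clear) go to sub-arm A or B on the screening result, and for Arm 2 "All women that are eligible for ablative treatment will be treated and randomised". Only one Module 1 group is randomised after histology: "Women with CIN2+ on biopsy who have not been treated based on screening results from arm 1 will also be randomised", provided they are eligible for ablation.

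Section 4.3 follows Module 1 women to 12 months and Module 2 women to 12 and 24 months.

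**The concern.** Most of the 143 have no histological diagnosis when they are allocated and treated, so the sentence in section 2.1, taken at its word, does not describe them. The text says that these women can be directed or invited to Module 2, which could mean a fresh enrolment, but a woman already ablated cannot be randomised again to a first ablation. The six-month prior-treatment exclusion in section 4.1.2, headed for both modules, would also catch her if it applied a second time.

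The Module 1 A:B ratio is not printed, and no schedule is named for women who belong to both modules. If the 97 did not count, the primary cure-rate comparison would lose about two thirds of the Module 1 contribution, and 777 outside cases would not deliver the stated 80% power.

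**Working it through.** **Inputs.** Section 3.5.1: 3000 women, HSIL+ prevalence 5%, HPV test sensitivity 95%, 4:1 allocation, VIA sensitivity 75%, ablation eligibility 85%. Section 3.9.1: cure 70% versus 80%, two-sided 0.05, 80% power, 20% attrition, 20% ineligible. Section 3.8: 1:1 allocation.

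**The plan's own figure.** A two-sided Z-test of proportions with pooled variance and no continuity correction gives 294 per arm, or 588 in all; Table 6 has 589. Then 589 / 0.80 = 736 randomised and 736 / 0.80 = 920 cases. The 920 reproduces.

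**Splitting the 143**
- HSIL+ and HPV positive: 3000 x 0.05 x 0.95 = 142.5, of which 114 are in Arm 1 and 28.5 in Arm 2.
- Randomised before histology: 114 x 0.75 x 0.85 = 72.7 in Arm 1, plus 28.5 x 0.85 = 24.2 in Arm 2. Total 96.9.
- VIA-negative, eligible, randomised after histology: 114 x 0.25 x 0.85 = 24.2.
- Ineligible for ablation: 142.5 x 0.15 = 21.4.

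The 97 is derived, not printed. Removing the 4% of Arm 1 with suspected cancer or inadequate VIA gives 93 to 94. If the 20% attrition all falls before treatment, it is 0.80 x 96.9 = 78.

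**Outside cases.** 777 x 0.80 = 621.6 randomised.

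| Reading | Module 1 women randomised | All randomised | Evaluable (x 0.80) | Power |
|---|---|---|---|---|
| Module 1 allocation counts | 96.9 + 24.2 = 121.1 | 742.7 | 594 | 80.5% |
| Section 2.1 sentence taken literally, recruitment stops at 777 | 24.2 | 645.8 | 517 | 74.8% |

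The first row meets the planned 736 randomised and 589 evaluable. If the Module 1 women are given Module 2's 80% eligibility instead of 85%, it becomes 621.6 + 142.5 x 0.80 = 735.6 randomised and power is 80.1%. Under the second row, reaching 736 would take (736 - 24.2) / 0.80 = 890 outside cases.

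**Which reading the text supports**
- Sections 3.2.1, 3.9 and 4.2 use one pair of labels for the treatment arms: A for cryotherapy and B for thermal ablation.
- The Module 1 biopsy precedes ablation, so it records disease status at baseline even though the report arrives later. Restricting the comparison to women with CIN2/3 on that biopsy selects on tissue taken before treatment, which leaves the randomised comparison intact.
- Section 3.2.1 recalls all treated Module 1 women at 12 months for HPV testing, VIA, and colposcopy with biopsy in HPV positives. Section 3.8 gives Module 2 women the same assessment, so the primary outcome is collected whether or not a woman later accepts an invitation.
- Where allocation is unequal (4:1, 3:1) the protocol says so. The silence on A:B in Module 1 sits most easily with the 1:1 of section 3.8.

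**The case for a change.** The best case for acting is that entry to the primary randomised comparison, and the allocation it uses, belong in the protocol, and that a few sentences would settle the matter at no cost. It is true that carry-over is not stated in the visible text, that the section 2.1 sentence does not fit about 97 women as worded, and that inviting women after treatment could make entry selective. Those observations stand.

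They do not amount to a defect in the design. The section 2.1 sentence is an overview in the background. Sections 3 and 3.8 require only HIV positive women with CIN2/3, and section 4.1 contains no rule that histology must precede randomisation. The six-month exclusion is headed as a criterion for taking part in CESTA and is most naturally about treatment before the study. Selective entry is no threat to the 12-month endpoint, because that visit is already due under Module 1.

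On follow-up, the Executive Summary says that CIN2/3 women randomised in Module 2 are invited at one and two years. A Module 1 woman who joins would ordinarily follow that schedule. Figures 2 and 4, where movement between the modules is most likely drawn, are not available, so the silence can be confirmed only for the text.

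**Conclusion.** The concern does not call for a change. All 143 are credited, and roughly 78 to 97 of them, depending on where attrition and inadequate VIA fall, are allocated before histology. Under the reading that the shared labels and the biopsy timing support, the 920, the 777 and the 80% power all hold, with computed power between 80.1% and 80.5%.

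The drop to about 75% needs two further assumptions. One is that a background sentence overrides the module descriptions. The other is that outside recruitment stops at 777, although section 3.8 sets the requirement at 920 and offers 143 and 777 only as estimates. If Module 1 supplied fewer usable women, recruitment to 920 would have to continue.

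Analysts would use the A/B allocation already received, restrict to CIN2/3 on the pre-treatment biopsy, and apply the Module 2 visits. Writing that down would alter no sample size, power or primary result. This conclusion assumes that carry-over is intended and that the Module 1 treatment allocation is 1:1.

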colposcopy for appropriate management. Similar to Module 1, women will be called by telephone after 1 week and 1 month to assess side-effects and satisfaction with the treatment. All women who were CIN2/3 and were randomized to ablative treatment or referred to colposcopy will be invited for a 1 year and 2 year follow-up visit. Similar as in Module 1, Women will be screened with HPV testing and VIA and 2-4 colposcopy-directed biopsies will be taken from all HPV positive women. Women with remaining/recurrent CIN2+ disease will receive appropriate management.

The cost-effectiveness study will assess the comparative value and efficiency of the two treatment methods.

2. Background

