2.5.1. Cryotherapy

Cryotherapy consists of freezing the lesion and underlying tissue to a temperature of at least -20° Celsius. The treated tissue necrotises and is replaced by new healthy epithelium. A reusable probe is applied to the cervix and the freezing is obtained through decompression of either carbon dioxide (CO2) or nitrous oxide (N2O) gas. The main side-effect is a watery vaginal discharge for up to 2-3 weeks, which is generally well tolerated. The equipment is simple, no electricity is needed and the technique is relatively easy to perform. Cryotherapy can be provided by a variety of healthcare personnel including general doctors, nurses, midwives and auxiliary health workers who can be trained in short sessions. For those reasons, cryotherapy is very suited for LMIC. In addition, it can also be used in a single visit screen-and-treat approach in combination with a screening test that provides immediate results, such as VIA. One potential impediment of the technique is the inadequate availability or elevated cost of the freezing gas. Lesions that are not eligible for cryotherapy are those that reach >2mm in the endocervical canal; are larger than the cryoprobe; cover more than 75% of the ectocervix; and should be treated with LLETZ. Lesions that are suspicious of invasive cancer should be biopsied and treated according to diagnostic work up.

A meta-analysis showed that cryotherapy is 92% and 85% effective to eliminate CIN2 and CIN3, respectively (cure : normal cytology at follow-up) [15].

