3.9. Statistical methods Module 2 Cure rate study

For primary objective 1, we will compare the CIN2/3 cure rates of treatment with cryotherapy (Arm A) or thermal ablation (Arm B) after 12 months of treatment among HIV positive women using Z-test for comparison of proportions in intention-to-treat and per-protocol analyses.

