4.3. Duration of subject participation

For all women, the study will include one round of HPV testing. HPV negative women will finish their participation in the study after this first round.

In Module 1, all HPV positive women with or without VIA triage will have a follow-up HPV test at 12 months, and will end their participation if the HPV test at 12 months is negative or after <CIN2 histology on biopsy collected at the colposcopy visit or after treatment (LLETZ or other) for CIN2+.

In Module 2, women with CIN2/3 on biopsy will be randomized into TA or cryotherapy. Women that are ineligible for ablative treatment will be referred to colposcopy for appropriate management and all other women with LSIL+ cytology will be exited from the study and referred back to the ARV clinic for follow up according to South African standard of care. All treated women will attend a FU visit at 12 mo. and 24 mo. with HPV testing, VIA, and colposcopy-directed biopsies on HPV positive women to detect remaining/recurrent disease. At the time of exit, all women will be given clear indications on how to continue with regular screening or with any needed follow-up under the local health system.

5. Ethical considerations

The study will be approved by the IARC and local ethical committees of participating countries: currently being the Biomedical Research Ethics committee (BREC) at the University of KwaZulu-Natal and the "Comité National d'Ethique pour la Recherche en Santé" under the Ministère de la Santé et de l'Action Sociale, Dakar. All women in the study will sign informed consent forms approved by IARC's and the local ethical committees.

The informed consent form will include details on the background, procedures of the study, risks and benefits, statement of confidentiality, specimen use and study staff to contact (informed consent document in annex).

The study is considered minimal risk and the procedures are standard practice in cervical cancer screening programs. The clinical procedures to be performed were developed by a team of clinicians including colposcopists mainly considering the safety of the participants in terms of reduction of cervical cancer risk, and all the procedures are consistent with standard medical practice and/or WHO recommendations, including thermal ablation.

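### Module 2 sets its 12- and 24-month recall by randomisation in the summary but by treatment in sections 3.8 and 4.3, so a woman randomised but not treated may have no visit to supply her intention-to-treat outcome

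*Protocol*

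**What the plan says.** Three places in the protocol say who returns for follow-up in Module 2.

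- Executive summary (section 1, Module 2): "All women who were CIN2/3 and were randomized to ablative treatment or referred to colposcopy will be invited for a 1 year". Membership is set by randomisation or referral; the same sentence adds a visit at two years.
- Section 3.8 (study outline): "In addition, all treated women will be recalled at 12 and 24 months for a follow-up visit including HPV testing, VIA, colposcopy and biopsy". Membership is set by treatment.
- Section 4.3 (duration of participation): "All treated women will attend a FU visit at 12 mo. and 24 mo". Again by treatment.

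Section 3.7.1 places the primary endpoint "12 months after the treatment in HIV positive women". Section 3.9 says the arms will be compared "using Z-test for comparison of proportions in intention-to-treat and per-protocol analyses". At the follow-up visits, cure is judged from HPV testing and VIA, with colposcopy-directed biopsies in HPV-positive women.

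**The concern.** The two descriptions do not define the same group. A woman randomised to cryotherapy or thermal ablation who then receives neither, nor any other treatment, is inside the summary's group and outside the group in sections 3.8 and 4.3. A clinic working from the study outline would have no instruction to recall her.

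The 12-month cure status comes only from the follow-up visit. If none is scheduled, her outcome is absent because of the protocol's wording and not because she was lost. An analysis plan can say how missing outcomes are handled, but it cannot recover a visit that was never scheduled. To that extent the primary comparison would be conditioned on something that happens after randomisation, namely receipt of treatment, which intention-to-treat is meant to avoid.

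**Working it through.** **Passages side by side**

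| Woman with CIN2/3 | Executive summary | Sections 3.8 and 4.3 | Needed for the section 3.9 ITT analysis |
|---|---|---|---|
| Randomised, given the allocated ablation | invited | recalled | yes |
| Randomised, given another treatment | invited | recalled (she is treated) | yes |
| Randomised, given no treatment | invited | not mentioned | yes |
| Referred to colposcopy, then treated | invited | recalled, if treated covers referral treatment | no (not randomised) |
| Referred to colposcopy, never treated | invited | not mentioned | no (not randomised) |

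Only the third row affects the primary comparison. The last two rows concern consistency of follow-up.

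**How many women could be in the third row**

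The protocol gives no rate. By section 3.8, eligibility for ablation is assessed first, then the woman is randomised 1:1, and the nurse treats at the same visit. There is little time for a woman to be randomised and left untreated.

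About 143 of the 920 women are expected from Module 1. Section 4.3 gives all HPV-positive women in that module an HPV test at 12 months whatever their treatment. The gap therefore mainly concerns the other 920 − 143 = 777, who are recruited directly.

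**The plan's own figure**

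Section 3.9.1: cure 70% against 80%, two-sided 0.05, power 80%.

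n per arm = [1.960·√(2 × 0.75 × 0.25) + 0.842·√(0.70 × 0.30 + 0.80 × 0.20)]² / 0.10² ≈ 293.1, rounded up to 294, or 588 in total. Table 6 states 589. Then 589 / 0.8 ≈ 736 and 736 / 0.8 = 920, as stated. The sample size reproduces, and the point does not depend on it.

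**Illustration under an assumed untreated share u**

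Base: 920 × 0.8 / 2 = 368 randomised per arm; with 20% attrition, 368 × 0.8 ≈ 294 evaluable; power 80.2%. Assume u is the same in both arms.

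| u (assumed) | Untreated per arm | Power if dropped | Power if counted as not cured |
|---|---|---|---|
| 1% | 3.7 | 79.8% | 78.6% |
| 2% | 7.4 | 79.4% | 77.0% |
| 5% | 18.4 | 78.1% | 72.2% |
| 10% | 36.8 | 75.9% | 64.6% |

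For the estimate, let untreated women clear their lesions at the same rate c in both arms. The full ITT difference is [0.80(1 − u) + cu] − [0.70(1 − u) + cu] = 0.10(1 − u). That is 9.8 points at u = 2%, 9.5 at 5% and 9.0 at 10%, against 10 points if these women are dropped. Within this symmetric assumption the shift is at most 1 point over the range.

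**The case against.** The best reply is that the wordings cover nearly the same women. Neither section 3.8 nor section 4.3 says that *only* treated women return. In section 4.3 the sentence follows the exit of women without CIN2/3, so it can be read as shorthand for everyone who stays in. In Module 1, section 3.2.1 also recalls all treated women, although the executive summary and section 4.3 set that visit for all HPV-positive women; this suggests the phrase is used loosely. Treatment at the randomisation visit leaves few women untreated, and 20% attrition is already planned. The Module 2 flowchart, which might settle the matter, is not shown.

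Most of this stands, and it limits the point to a small one. It does not remove it: the operative sections still name a narrower group than the summary, and nothing in the text shown says which governs.

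Four stronger readings are tempting, and the protocol does not support them.

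- *ITT and per-protocol could not differ.* They could. A woman given a treatment other than her allocation is treated and recalled. She counts in her assigned arm under ITT and may be left out per protocol.
- *Loss would fall on the cryotherapy arm.* Section 2.5.1 does say "One potential impediment of the technique is the inadequate availability or elevated cost of the freezing gas", but that is general background. Nothing predicts non-delivery at the trial clinics, let alone in one arm only.
- *Follow-up of 184 women (20% of 920) is at stake.* Section 3.8 refers ineligible women for management and treatment, so only those never treated would be in doubt. They are not randomised and do not enter the primary comparison. The protocol's own count of ineligible women is 146.
- *The extra visits are already paid for.* The protocol gives no visit budget.

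**Conclusion.** The contradiction is real. On the plain reading of sections 3.8 and 4.3, a directly recruited woman who is randomised and receives no treatment has no scheduled outcome visit, and the ITT analysis in section 3.9 would lack her result by design.

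The effect is probably small. It rests on an untreated share that the protocol does not give and that same-visit treatment should keep low. The power figures and the shift of up to 1 point assume equal shares of 1% to 10% in both arms; they show scale and are not estimates. No direction or size of bias between the arms can be derived from the document. The point is worth acting on because it concerns the primary endpoint and is easy to correct before follow-up begins.

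**What to change.** Reconcile sections 3.8 and 4.3 with the executive summary so that one Module 2 follow-up population is stated throughout. For the primary comparison, define the 12- and 24-month outcome visits by randomisation to cryotherapy or thermal ablation, not by receipt of treatment, since the ITT analysis in section 3.9 requires it. As the endpoint is timed from treatment, also state the date from which the visits are counted for a randomised woman who was not treated. In each place, say in the same terms whether women referred to colposcopy are followed. Check the Module 2 flowchart against the agreed text.

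This concerns outcome ascertainment only and leaves clinical management as it is. The cost is wording in two sections, plus the follow-up visits of a probably small number of untreated women. The sample size does not change.
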